6. INVESTIGATION PLAN

6.1 Overall Study Design and Plan Description

This is an exploratory phase II, open-label, randomized, multicenter, parallel group trial to determine whether there is evidence that the addition of either or both different dose levels of CX-01 to standard induction therapy (idarubicin + cytarabine) and consolidation therapy has an additive therapeutic effect in newly diagnosed AML patients when compared to patients receiving standard induction chemotherapy alone.

Approximately 75 patients will be randomized in a 1:1:1 ratio to one of the following treatment groups:

- **Group 1:** Idarubicin + Cytarabine, OR
- **Group 2:** Idarubicin + Cytarabine plus lower dose CX-01 (0.125 mg/kg/hour), OR
- **Group 3:** Idarubicin + Cytarabine plus higher dose CX-01 (0.25 mg/kg/hour)

Eligible patients who meet the inclusion criteria and do not meet any of the exclusion criteria and have provided informed consent will be enrolled in the study. Each patient will participate in the study for approximately 18 months from the time of informed consent through final study contact, or until they withdraw from the study or the study is terminated by the Sponsor.

[figure not shown]
Overall survival data will be collected every 3 months until death or until the end of study by the investigational sites. The end of study will occur approximately 18 months after the last patient is randomized.

A Data and Safety Monitoring Committee (DSMC) will meet periodically to review the safety of the study (see Section 6.6.5). Details describing the DSMC process and procedures will be outlined in a separate DSMC Charter.

Adverse events (AEs) will be collected from time of informed consent and continue until 30 days after the last study treatment is administered. Longer follow-up and collection of AEs may be required for patients that do not have an absolute neutrophil count (ANC) recovery within 42 days (i.e., until the recovery or the reason for no recovery is diagnosed) after the last induction or consolidation cycle.

A flow diagram of the study design is shown in Figure 6—1.

Figure 6—1 Study Design

Abbreviations: AML=acute myeloid leukemia

Note: It is expected that approximately 90 patients will be screened to identify 75 patients for randomization.

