6.6.3 Safety Assessments

Key safety endpoints will be assessed by review of summaries of AEs which will include only treatment-emergent AEs (TEAEs), unless otherwise stated. Adverse events will be categorized by System Organ Class (SOC) and preferred term using the Medical Dictionary for Regulatory Activities (MedDRA) dictionary (version 14.1), and will be graded according to NCI-CTCAE version 4.03.

6.6.3.1 *Adverse Events*

Adverse events will be monitored throughout the study. Adverse events will be collected from the time of informed consent and continue until 30 days after the last study treatment is administered. Longer follow-up and collection of AEs may be required for patients who do not have an ANC recovery by Day 42 (i.e., until the recovery or until a reason for no recovery is diagnosed) after the last induction or consolidation cycle.

For the purpose of this study, the terms toxicity and AE are used interchangeably.

6.6.3.2 *Definitions*

6.6.3.2.1 *Definition of an Adverse Event*

In a clinical study, an AE is any untoward medical occurrence (i.e., any unfavorable and unintended sign [including abnormal laboratory findings], symptom, or disease) in a patient or clinical investigation subject after providing written informed consent for participation in the study. Therefore, an AE may or may not be temporally or casually associated with the use of a medicinal (investigational) product.

A surgical procedure that was planned prior to the start of the study by any physician treating the subject should not be recorded as an AE (however, the condition for which the surgery is required may be an AE).

In the following differentiation between medical history and AEs the term “condition” may include abnormal symptoms, diseases, laboratory, or vital sign findings.

- Conditions that started before signing of ICF and for which no symptoms or treatment are present until signing of ICF are recorded as medical history (e.g.,

seasonal allergy without acute complaints)

- Conditions that started before signing of ICF and for which symptoms or treatment are present after signing of ICF, at unchanged frequency and/or intensity, are recorded as medical history (e.g., allergic pollinosis)
- Conditions that started or deteriorated after signing of informed consent will be documented as AEs.

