Abnormal laboratory and other abnormal investigational findings (i.e., physical exam) should not be reported as AEs unless they are associated with clinical signs and symptoms, lead to treatment discontinuation or are otherwise considered clinically relevant by the Investigator. In cases of surgical or diagnostic procedures, the condition/illness leading to such a procedure is considered as the AE rather than the procedure itself. In a case of fatality, the cause of death is considered as the AE, and the death is considered as its outcome.

Medical conditions/diseases present before starting study drug are considered to be an AE only if they worsen after starting study drug and are clearly not related to cytarabine and/or idarubicin toxicities, or to AML that is not yet in remission. Abnormal laboratory values or test results constitute AEs only if they induce clinical signs and symptoms, are considered clinically significant, or require therapy.

Information about all AEs, whether volunteered by the patient, discovered by the Investigator or designee questioning, or detected through physical examination, laboratory test or other means, will be collected and recorded, as appropriate.

As far as possible, each AE should be evaluated to determine:

- The severity grade based on NCI-CTCAE version 4.03 (Grade 1 to 5)
- The relationship to the study drug(s) (see Section 6.6.3.2.6). A relationship between the AE and the underlying AML, the dose-intensive chemotherapy, and CX-01 treatment, will be assessed
- The duration (start and end dates or continuing at final contact)
- Action taken (no action taken, study drug dosage adjusted/temporarily interrupted, study drug permanently discontinued due to this AE, concomitant medication taken, non-drug therapy given, hospitalization/prolonged hospitalization, see Section 6.6.3.2.7)
- Whether it constitutes an SAE.

All AEs will be treated appropriately. Such treatment may include changes in study drug

treatment as listed in the dose modification section of the protocol (Section 6.4.4.2). Adverse events will be followed until resolution or stabilization of the event, completion of the patient's participation, or study termination, or the Investigator or designee and Sponsor agree that follow-up is no longer necessary, whichever occurs first.

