6.6.4.1 Expected Adverse Events

Myelosuppression and its associated complications due to underlying leukemia and/or intensive anti-leukemia therapy are expected events during therapy for AML.

Hospitalization or prolongation of hospitalization for the treatment of the following events that are known to be associated with myelosuppression from leukemia and/or intensive leukemia therapy, are also considered to be expected. These events still need to be recorded as AEs on the eCRF:

- Fatigue, weakness and/or shortness of breath associated with anemia
- Febrile neutropenia
- Bleeding due to thrombocytopenia e.g., epistaxis, gastrointestinal bleeding
- Bacteremia, sepsis, or other infections
- Neutropenic colitis.

Death due to progression of AML and/or its associated complications are expected in the patient population and are listed in Appendix E. Deaths should be reported with Investigator's assessment of causality.

Appendix E also contains a list of known/expected AEs for cytarabine and idarubicin. The IB contains expected events known for CX-01 (63).

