7.7 Safety

7.7.1 Adverse Events

All adverse events (AEs) recorded on the eCRF will be coded using the MedDRA dictionary [Version 14.1] and classified as either pre-treatment AEs or treatment-emergent AEs (TEAEs) as follows:

- Pre-treatment AEs are events that start prior to the date of first dose of study treatment.
- Treatment-emergent AEs (TEAEs) are events with start date and time on or after the date and time of first dose of study treatment (and up to 30 days after date of last dose of treatment) with

Statistical Analysis Plan

Version: Final

Date of Issue: 20 March 2018

Cantex Pharmaceuticals, Inc. Protocol No. CNTX-CX-01 2015 AML I Covance Study ID: 00000014620 I

start date prior to the date of first dose of study treatment whose severity worsens on or after the date and time of first dose of study treatment.

Assessment of AE severity will be based on the National Cancer Institute-Common Terminology Criteria for Adverse Events (NCI-CTCAE, version 4.0.3).

All AE data will be listed by treatment group including Pre-treatment AEs and TEAEs. The number and percentage of subjects reporting each treatment AE and TEAEs will be summarized for each treatment group and overall, by System Organ Class (SOC) (sorted alphabetically) and Preferred Term (**PT**) (sorted by descending overall total) for Safety populations.

In addition, corresponding listings of serious AEs (SAEs), AEs leading to discontinuation of treatment, AEs causing interruptions from study treatment, AEs causing dose reduction from study treatment and study treatment-related AEs causing dose reductions are provided.

An overview table will summarize the number and percentage of subjects with at least one of the following AEs/TEAEs, where subjects with more than one AEs/TEAE in a particular category are counted only once in that category:

- any AE;
- any TEAEs;
- treatment-related TEAE;
- any AE by maximum NCI-CTCAE grade; treatment-related TEAE by maximum NCI-CTCAE grade;
- AE leading to treatment interruption;
- treatment-emergent AEs leading to treatment interruption;
- AE leading to treatment reduction;
- treatment-emergent AEs leading to treatment reduction;
- AE leading to treatment discontinuation; treatment-emergent AEs leading to discontinuation from the study;
- SAE;
- treatment-emergent SAE;
- SAE leading to death;
- treatment-emergent SAE leading to death;
- SAE leading to treatment discontinuation;

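### Protocol 6.6.3.2.1 lets an open-label causality opinion decide whether worsening of a pre-existing condition is recorded as an AE, contradicting its own general rule and the SAP's TEAE definition

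*Protocol*

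**What the plan says.** Protocol section 6.6.3.2.1 (Definition of an Adverse Event) contains two rules for a condition the patient already has.

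- The general rule has no causality test. The opening definition states that "an AE may or may not be temporally or casually associated with the use of a medicinal (investigational) product", and the list separating medical history from AEs ends with "Conditions that started or deteriorated after signing of informed consent will be documented as AEs".
- Later in the section, the rule for conditions that predate treatment is narrower: "considered to be an AE only if they worsen after starting study drug and are clearly not related to cytarabine and/or idarubicin toxicities". The same sentence then adds a second exclusion, which reads "or to AML that is not yet in remission".

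The section then treats attribution as a separate step for each AE: "A relationship between the AE and the underlying AML, the dose-intensive chemotherapy, and CX-01 treatment, will be assessed".

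Two other places in the protocol point towards recording. Section 6.6.4.1 lists complications of myelosuppression from leukemia or its treatment and adds: "These events still need to be recorded as AEs on the eCRF". Appendix E lists events expected with cytarabine and idarubicin and sends them through routine AE or SAE reporting.

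In SAP section 7.7.1, an event that began before the first dose is treatment-emergent if it is one "whose severity worsens on or after the date and time of first dose of study treatment". No attribution condition is attached.

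On design, section 6.1 states: "This is an exploratory phase II, open-label, randomized, multicenter, parallel group trial". Section 5.1 makes safety and tolerability a primary objective, and section 6.6.3 assesses the key safety endpoints from TEAE summaries.

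**The concern.** An AE definition should fix what is recorded, and causality should be judged afterwards. The restrictive sentence reverses that order for one class of event. Its threshold is also demanding: the worsening must be clearly not due to chemotherapy or unremitted AML, so an uncertain case is left out by default. Every patient receives chemotherapy, and every patient has active AML during induction.

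Two things are at stake. First, a worsening that is not entered cannot be recovered from the AE data by any later analysis. Second, the person judging knows the treatment arm, and CX-01 is a possible cause only in Groups 2 and 3, so the judgement could differ by arm. Sites that follow different sentences of the same section would also record different data.

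**Working it through.** The plan gives no rate or count on this point, so it has no figure of its own to reproduce here. Its one design figure, 71.8% power with 25 per arm, concerns the CR comparison. Exact enumeration of the one-sided Fisher test at 0.15 for 0.55 versus 0.80 gives 0.717, and no change to the AE definition alters it. The check is therefore a comparison of texts, followed by an illustration of direction.

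**Step 1: the rules side by side.**

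| Place | Trigger | Timing | Causality test |
|---|---|---|---|
| Protocol 6.6.3.2.1, general rule | condition starts or deteriorates | after consent | none |
| Protocol 6.6.3.2.1, restrictive sentence | pre-existing condition worsens | after study drug starts | clearly not chemotherapy, nor AML not in remission |
| Protocol 6.6.4.1 | listed myelosuppression complications | not stated | recorded although due to leukemia or its treatment |
| Protocol Appendix E | listed events expected with cytarabine or idarubicin | not stated | reported although attributed to these drugs |
| SAP 7.7.1 | earlier event worsens in severity | on or after first dose | none |

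The restrictive sentence differs from the general rule in two ways: it adds a causality test, and it starts the clock later.

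**Step 2: one case under each rule.** Section 6.3.1 admits patients with raised AST or ALT below 2.5 x ULN. Suppose such a value rises to Grade 2 (above 3 to 5 x ULN in section 6.4.4.2), is judged clinically relevant and is not serious. The general rule makes it an AE. Appendix E lists ALT and AST, Grades 1-4, for both chemotherapy drugs and routes them to AE reporting. The restrictive sentence excludes it unless chemotherapy is clearly not the cause, which could rarely be said. Yet liver enzymes matter for CX-01 too: Table 4-1 reports AST and ALT changes with it, and section 7 names abnormal liver tests as a heparin class effect.

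**Step 3: where the record would have gone.** The SAP shells plan AE tables by attribution: 14.3.1.2 (idarubicin), 14.3.1.3 (cytarabine), 14.3.1.4 (CX-01) and 14.3.1.5 (underlying disease or other drugs). A worsening excluded because chemotherapy or AML may have caused it belongs in 14.3.1.2, 14.3.1.3 or 14.3.1.5. One to which CX-01 also contributed would be missing from 14.3.1.4.

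**Step 4: possible direction of bias.** All rates here are assumptions. With 25 patients per arm,

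recorded rate = true rate x (1 - share not recorded).

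| True rate, control / CX-01 | Share not recorded, control / CX-01 | Recorded, control / CX-01 | Difference (CX-01 minus control) |
|---|---|---|---|
| 20% / 40% (5 / 10 patients) | 0 / 0 | 20% / 40% | +20 points |
| 20% / 40% | 50% / 50% | 10% / 20% | +10 |
| 20% / 40% | 80% / 80% | 4% / 8% | +4 |
| 20% / 40% | 50% / 80% | 10% / 8% | -2 |
| 20% / 40% | 80% / 50% | 4% / 20% | +16 |
| 30% / 30% | 80% / 50% | 6% / 15% | +9 |
| 30% / 30% | 50% / 80% | 15% / 6% | -9 |

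For example, 0.40 x (1 - 0.80) = 0.08. Equal filtering shrinks a real difference. Unequal filtering can reverse a real difference or create one where none exists, in either direction.

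**The case against.** The strongest reply is that the sentence is narrow and is surrounded by contrary instructions.

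- It covers only conditions present before study drug; new-onset events are untouched.
- SAEs are reported whatever their attribution (6.6.3.2.2 and 6.6.4).
- Section 6.6.4.1 and Appendix E expressly require recording of many events caused by chemotherapy or leukemia.
- Mortality at 30, 60 and 90 days and platelet recovery are separate endpoints.
- By-visit laboratory summaries and the coagulation and platelet graphs (SAP 7.7.2) do not depend on AE status. The CTCAE-grade shift shells are an exception, since they appear to draw on AE pages.
- Safety analysis is descriptive, in an exploratory trial.

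All of this stands and limits the scope. It does not remove the contradiction, because a site obeying the restrictive sentence would still omit events that the general rule requires.

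Three stronger readings are tempting, and the documents do not support them.

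- A reader might infer that almost no worsening would ever be entered. That assumes sites follow one sentence over several that say otherwise. The AML limb also falls away once a patient is in remission for consolidation, although the cytarabine limb remains.
- A reader might infer a false excess of events on CX-01. But chemotherapy is present in all three arms, and a further candidate cause does not make it clearly not responsible. Near-total filtering in every arm would mean under-recording, not imbalance.
- A reader might infer that the bleeding signal is lost. Section 6.3.2 excludes significant active bleeding, anticoagulant therapy and known bleeding or coagulation disorders. Important on-study bleeding would therefore mostly be new-onset, and section 6.6.4.1 names bleeding due to thrombocytopenia among the events to record.

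**Conclusion.** The concern holds as an internal contradiction with a limited but real consequence. The restrictive sentence in 6.6.3.2.1 conflicts with the general rule in the same section, sits badly with 6.6.4.1 and Appendix E, and does not fit the SAP's TEAE definition. If followed, the data at risk are mainly non-serious worsening of baseline conditions in the TEAE and attribution tables.

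The size of the loss cannot be derived, because the documents give neither the rate of worsening nor the share that would be left out. The direction of any difference between arms is equally unknown, and masking a CX-01 signal is as possible as creating one. The illustration rests wholly on assumed rates and shows only that both can happen. The primary efficacy test is unaffected. This should be fixed, since safety is a primary objective and omitted events are hard to reconstruct later.

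**What to change.** Rewrite the sentence in section 6.6.3.2.1 so that a condition present before study drug is recorded as an AE if it worsens after informed consent, whatever the suspected cause. This takes two edits:

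1. Delete the clause on chemotherapy toxicity and AML.
2. Replace the start of study drug with informed consent as the time reference. Deleting the clause alone would leave the timing in conflict with the general rule. It would also leave an ambiguity for control patients, because section 6.4.2.1 uses study drug to mean CX-01.

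Record relationship to AML, chemotherapy and CX-01 only in the causality assessments already planned (6.6.3.2.1 and 6.6.3.2.6). SAP 7.7.1 already separates pre-treatment AEs from TEAEs, so worsening between consent and first dose need not enter the TEAE tables.

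The cost is one protocol sentence, a memo so that all sites apply the same rule, and somewhat more AE entries.

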6.6.3.2.3 Suspected Unexpected Serious Adverse Reactions

Suspected unexpected serious adverse reactions (SUSARs) are serious events that are not listed in the IB. Suspected adverse reactions means any AE for which there is a reasonable possibility that the drug caused the AE. For the purposes of Investigational New Drug (IND) safety reporting, 'reasonable possibility' means there is evidence to suggest a causal relationship between the drug and the AE.

6.6.3.2.4 Follow-up of Adverse Events/Serious Adverse Events

Adverse events will be followed until resolution or stabilization of the event, completion of the patient's participation, or study termination, or the Investigator or designee and Sponsor agree that follow-up is no longer necessary, whichever occurs first.

Serious AEs will be followed until resolution, the condition stabilizes, or the Investigator or designee and Sponsor agree that follow-up is no longer necessary.

All AEs will be immediately recorded in the patient's source documents.

6.6.3.2.5 Assessment of Severity

The severity grade will be based on the NCI-CTCAE version 4.03. An electronic copy of the CTCAE Version 4 can be downloaded from: <http://safetyprofiler->

ctep.nct.nih.gov/CTC/CTC.aspx.

6.6.3.2.6 *Causality Assessment*

The Investigator must assess and document causal relationship between an SAE and the study drug on the basis of his/her clinical judgment using the following definitions. The causality assessment must be made based on the available information and can be updated as new information becomes available.

Is there a “reasonable possibility” the drug caused the AE (meaning there is evidence to suggest a causal relationship between the drug and the AE)?

- Yes
- No.

Could the AE be explained by underlying disease or other drugs or chemicals?

- Yes
- No.

6.6.3.2.7 *Action Taken Regarding the Study Drug*

- **No action taken:** no change in treatment dosage
- **Dose reduction:** study drug dosage adjusted/or and reduced
- **Drug interrupted:** study drug temporarily stopped
- **Drug withdrawn:** study drug permanently stopped
- **Specific treatment instituted:** other concomitant medication or non-drug therapy administered in response to an AE.

6.6.3.2.8 *Adverse Event Outcome*

- **Recovered/resolved:** the patient fully recovered from the AE with no residual effect observed
- **Recovered/resolved with sequelae:** the residual effects (e.g., symptoms or pathology) of the AE are still present and observable
- **Not recovered/not resolved:** the AE itself is still present and observable
- **Fatal:** the patient dies as a result of the AE

- **Unknown:** outcome of the AE is unknown.

6.6.3.3 *Pregnancy*

Although not considered an AE, it is the responsibility of the Investigator or their designee to report any pregnancy in a patient or the patient's sexual partner that occurs during the study. All patients who become pregnant must immediately discontinue the study drug and be withdrawn from the study. The patient will be followed to completion/termination of the pregnancy. This information is important for both drug safety and public health concerns. If a patient is found to be pregnant after the study treatment was administered, the Investigator should report this to the CRO and Sponsor immediately and document using the Pregnancy Form.

The Investigator must make every effort to follow the patient until completion of pregnancy. If the outcome of pregnancy meets the criteria for classification of an SAE, the Investigator must follow the procedures for reporting SAEs outlined in Section 6.6.4.

6.6.3.4 *12-lead Electrocardiogram*

A standard resting 12-lead ECG will be performed at Screening and at the end of induction (Day 7). Additional 12-lead ECGs may be obtained at the Investigator's discretion or if clinically indicated.

6.6.3.5 *Left Ventricular Ejection Fraction*

An echocardiography or MUGA scan will be performed during Screening to determine the patient's cardiac ejection fraction for eligibility in the study.

6.6.3.6 *Laboratory Assessments*

The time points at which these samples will be collected are shown in the Schedule of Study Procedures (Table 6—1) and (Table 6—2). Assessments will be performed and evaluated locally.

The following clinical laboratory assessments will be performed:

- **Hematology panel:** hemoglobin , ANC, and platelet
- **Chemistry (comprehensive metabolic panel):** ALT, AST, total bilirubin, alkaline phosphatase , BUN, and serum creatinine
- **Coagulation panel:** anti-factor Xa, PT, aPTT, INR.

Any clinically significant abnormal laboratory value should be immediately re-checked whenever possible, for confirmation before making any decision for the concerned patient. It should be documented as an AE/SAE per protocol requirement.

A urine pregnancy test will be conducted at Screening for all females of childbearing potential to confirm absence of pregnancy. Positive urine test results must be confirmed by serum pregnancy test. Results will be analyzed locally. Pregnancy tests may be performed at other visits at the discretion of the Investigator.

6.6.3.6.1 *Bone Marrow Aspirate/Biopsy*

To evaluate disease status, a bone marrow aspirate and biopsy if needed will be done within 28 days before starting therapy. Bone marrow aspirate and biopsy will also be performed between Days 14-21 to determine the need for re-induction chemotherapy (see Section 6.4.1). Subsequent bone marrow examinations are specified in Section 6.5.1. Bone marrow aspirate at baseline and follow-up should include analysis by flow cytometry and cytogenetic analysis. Bone marrow (or peripheral blood if bone marrow is unavailable) should be sent to the institution's local cytogenetic laboratory for analysis.

For patients with documented CR, confirmatory bone marrow aspirate slides will be submitted to the Sponsor or designee.

6.6.3.7 *Vital Signs and ECOG Performance Status*

Measurement of vital signs will include an assessment of heart rate, BP, height, and weight. Height will be measured once during Screening. Weight will be measured at the beginning of each cycle to calculate treatment doses. Vital signs may be repeated for clinically significant abnormal findings at the discretion of the Investigator.

Eastern Cooperative Oncology Group performance status will be collected at Screening Visit only (see Appendix B).

6.6.3.8 *Physical Examination*

All abnormal findings on physical exam will be documented in the source documentation and eCRF. New or worsened abnormalities should be recorded as AEs, if applicable.

